Study Population:	Adult smokers in South Carolina and New York were recruited, with efforts to recruit people from lower socioeconomic status groups. Of 1818 people screened, 602 were ineligible, 773 either declined to participate or were unable to be scheduled for orientation, and 443 were eligible and randomized. Of these, 56 did not attend the study orientation, and 20 did not complete minimum criteria to be included in the analytic sample. The final analytic sample involved 367 people.
Description of Study Intervention/Experimental Manipulation:	The 2X2 between subject intervention involved randomization to one of four groups: a) control; b) inserts only; c) pictorial warnings only; d) inserts and pictorial warnings. Insert conditions included four rotating messages, two about cessation benefits and two with cessation tips. Warning text for all conditions included four rotating messages, with the text-only "control" condition used the current warning size and placement (i.e., 50% of one pack side), whereas pictorial warnings covered approximately 50% of the lower half of both the front and back of packs.
Study Duration:	June 28, 2019 to June 29, 2021
Participant Duration:	Study participation involved a 45-minute study orientation where potential participants completed a baseline survey, received training in the 14-day study, and were provided the study materials (i.e., smartphone, cigarette packs). After the 14-day observation period, participants completed a final survey and interview and received compensation.

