6 PARTICIPANT DISCONTINUATION/WITHDRAWAL

Participants could discontinue participation at any time. Clinically relevant findings were reported as an adverse event (AE). We discontinued participation for the following reasons:

- Significant study intervention non-compliance, as indicated by not logging any cigarettes or evening reports;
- Unable to contact study participant during any scheduled followup calls;
- Any event or medical condition or situation occurred such that continued collection of follow-up study data were not in the best interest of the participant or might have required an additional treatment that would confound the interpretation of the study.

The reason for participant discontinuation or withdrawal from the study were recorded. Those who signed the informed consent form and were randomized but did not receive the study intervention were replaced. Participants were also replaced if they signed the informed consent form, were randomized, received the study intervention, and subsequently withdraw, or if they were discontinued from the study.

A participant was considered lost to follow-up if study personnel were unable to contact the participant after at least 3 attempts. If the participant continued to be unreachable, he or she was considered to have withdrawn from the study with a primary reason of lost to followup.

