7 STUDY ASSESSMENTS AND PROCEDURES

7.1 ENDPOINT AND OTHER NON-SAFETY ASSESSMENTS

Participant data were collected in three phases: the baseline survey, which included measurement of potential moderators of intervention effects (H5 & H6); ecological momentary assessments across the 2-week study period, including data collected around smoking sessions and through daily evening surveys; the final followup survey. Specifics on each of these are provided below.

Baseline survey:

Participants with confirmed eligibility who consented to participate answered a baseline survey on sociodemographics (i.e., sex, education, income), a 1-minute validated task to assess

delay discounting,^{45 46} a health literacy assessment,¹¹⁴ and smoking-related perceptions and behavior (e.g., time to first cigarette; preferred brand; risk perceptions; quit intentions; readiness to quit; self-efficacy to quit) using validated questions.¹¹⁵⁻¹¹⁸ Participants were then trained in the EMA protocol and given a 14-day supply of their preferred brand of cigarettes with packs modified to reflect their experimental condition.

Ecological Momentary Assessment (EMA) protocol:

EMA data were collected from participants over 14 days using a study smartphone (Android, Samsung Galaxy J3 and Samsung Galaxy A10e) for which all functions were disabled except for the app used for entering data. Participants were asked to use the app to log every cigarette they smoked during this period. Approximately 4-5 times a day, participants were prompted to complete a brief, 1-3 minute survey immediately after they indicated that they had smoked, with cigarette logs sampled using an algorithm based on self-reported baseline smoking frequency to reduce participant burden. Each day, between 7 and midnight, an evening survey was available in the smartphone app, which took 1-3 minutes to complete. Participants received an alert on the study phone to complete this report at 9pm if they had not already completed it by that time. The app was programmed by [name]'s team at HBART and uploaded to the cloud in real time, which allowed for monitoring of participant compliance.

Follow-up survey and study debrief:

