- H5: Pictorial HWL effects (relative to text-only HWLs) on key outcomes (see H1) will be moderated by baseline self-efficacy to quit, such that the association will be stronger amongst smokers whose baseline self-efficacy is higher than lower (H5a). Moderation effects will be weaker when packs include inserts (H5b).
- H6: Insert effects will be moderated by education, literacy, and delay discounting, such that the association with key outcomes (see H1) will be stronger for smokers with higher education, higher literacy, and lower delay discounting than for their counterparts (H6a). Moderation effects will be weaker when inserts are accompanied by pictorial HWLs due to because pictorial HWLs will have stronger effects among smokers with lower education and lower literacy (H6b).

motivation to quit) were assessed for all hypotheses. Other outcomes are specific to pathways of influence for insert effects or, separately, for pictorial HWL effects; hence, some outcomes were assessed only when they were relevant to the labeling effect (insert vs. pictorial HWL) evaluated in the hypothesis. Similarly, the proxy measure of "reactance" (i.e., expressed reactance) was only assessed for hypotheses assessing whether insert effects reduce defensive responding (i.e., H1, H4). Finally, the two outcomes involving positive smoking experiences (i.e., satisfaction, cognitive elaboration of smoking benefits) were only relevant to the main effects of pictorial HWLs (H2). Table 3 lists all primary and secondary outcomes, showing which were assessed for each hypothesis. Appendix 1 includes results for outcomes that are not specific to hypotheses (i.e., do not have an X in the table below). Details on the specific measures used and frequency of assessment are provided in the outcomes and results section of clinicaltrials.gov.

Table 3. Outcomes assessed for each hypothesis

Outcome type	Outcome Variable name		H2	НЗ	H4	Н5а	H5b	Н6а	H6b
Primary	Self-efficacy to Quit Smoking	Χ		Χ	Х			Χ	Х
Primary	Self-efficacy to Cut Down on Smoking	Χ		Χ	Χ			Χ	Χ
Primary	Worry About Harms from Smoking		Χ			Χ	Χ		
Primary	Strength of Feeling About Smoking		Χ			Χ	Χ		
Primary	Extent of Motivation to Quit	Χ	Χ	Χ	Χ	Χ	Χ	Χ	Χ
Primary	Talk About Smoking Cessation or Harms	Χ	Χ	Χ	Χ	Χ	Χ	Χ	Χ
Primary	Foregoing/stubbing out a Cigarette	Χ	Χ	Χ	Χ	Χ	Χ	Χ	Χ
Secondary	Strength of Hopefulness About Quitting	Χ		Χ	Χ			Χ	Χ
Secondary	Satisfaction From Smoking		Χ						
Secondary	Cognitive Elaboration of Smoking Benefits		Χ						

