Secondary	Cognitive Elaboration of Smoking Harms		Χ			Χ	Χ		
Secondary	Cognitive Elaboration of Cessation Benefits	Χ		Χ	Χ			Χ	Χ
Secondary	Response Efficacy	Χ		Χ	Χ			Χ	Χ
Secondary	Perceived Susceptibility to Smoking Harms		Χ			Χ	Χ		
Secondary	Expressed Reactance Against Messages	Χ	Χ		Χ	Χ	Χ		
Secondary	Cigarettes Per Day (number of cig logs)	Χ	Χ	Χ	Χ	Χ	Χ	Χ	Х

X=included in the results data tables; results for outcomes that are not specific to hypotheses (i.e., no "X" in table above) are presented in data tables at the end of this document (see Appendix 1).

Assumptions for calculating power:

This section describes our assumptions regarding power before we collected our data. Throughout our discussion of power related to the statistical tests to evaluate our hypotheses of interest, we assume a moderate within-person autocorrelation of ρ = 0.40 for repeated measures. This estimate was lower than in the data we collected for this project (mean ICC=0.73) and in our re-assessment of preliminary data (mean ICC=0.72). Instead of running simulation programs to estimate power for mixed effects generalized linear models, we calculate the effective number of independent observations and use power for independence models.

Effective sample size: The effective number of independent observations $N_{\rm eff}$ is related to the number of correlated observations $N_{\rm eff}$ and the autocorrelation of correlated observations ρ as $N_{\rm eff} = N(1-\rho)/(1+\rho)$. Thus, our power calculations are derived using independence models with $N_{\rm eff} = 3N/7$ observations. Table 4 shows the effective sample for each hypothesis and data type, including adjustment for 10% and 20% missing data.

Table 4. Effective sample size for each hypothesis and data type, including missing data effects

				$N_{ m eff}$			
	Rep.			0% missing 10% missing 20% miss			
Data	Measures	Hypotheses	N	data	data	data	
Type 1	14	H1/H2	2,240=160*14	960	864	768	
	14	H3 ^{a-b} /H4 ^{a-b} /H5 ^{a-b} /H6 ^{a-b}	1,120=80*14	480	432	384	
Type 2	56	H1/H2	8,960=160*56	3,840	3,456	3,072	
	56	H3 ^{a-b} /H4 ^{a-b} /H5 ^{a-b} /H6 ^{a-b}	4,480=80*56	1,920	1,728	1,536	

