To test our study hypotheses (see Table 2, from Research Plan), we estimated a series of mixed effects generalized linear models, adjusting for repeated measures. The specific model we used depended on the type of dependent variable in the model. For each hypothesis, we estimated mixed effect generalized linear model of the outcome as a function of the inverse link: mixed-effects ordered logistic regression with inverse logit link for continuous/ordinal measures; mixed-effects regression with identity link for continuous/ordinal measures; negative binomial regression with log link for count measures; and mixed-effects logistic regression with inverse logit link for binary measures. Also, for outcomes with response options from 1 to 7, we estimated both mixed effects linear regression and ordered logistic regression models; however, we only report the results for the ordered logistic regression due to concerns about the distribution of responses and because the results are consistent across models. Note that the one count measure that we evaluate (i.e., cigarettes per day) is a single measure for each person and so there are no repeated measures. Evaluation of hypotheses will involve inference from Wald tests of associated regression parameters. We present power calculations for each hypothesis along with the model used to conduct the statistical tests. Subsequently, we discuss missing data and sensitivity analyses.

Throughout the following sections, we present models using the following indicator variables:

InsY _i	Person i has cigarette packages with inserts
$PicY_i$	Person i has cigarette packages with HWLs that include text and pictures
SeHi _i	Person i has a high baseline self-efficacy measure
EdHi _i	Person i has a high baseline education measure
$LtHi_i$	Person i has a high baseline literacy measure

Similarly, we also use the following indicator variables:

InsN _i	Person i has cigarette packages without inserts
$PicN_i$	Person i has cigarette packages with HWLs that include text only
$SeLo_i$	Person i has a low baseline self-efficacy measure
$EdLo_i$	Person i has a low baseline education measure
$LtLo_i$	Person i has a low baseline literacy measure

Model 1:

$$y_{ij} = g^{-1} \big[\beta_0 + (InsN_i \times PicN_i)\beta_1 + (InsN_i \times PicY_i)\beta_2 + (InsY_i \times PicN_i)\beta_3 + (InsY_i \times PicY_i)\beta_4 + Z_{ij}\tau + \gamma_i + \epsilon_{ij} \big]$$

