where g^{-1} is the inverse link function (identity for continuous measures, log for count measures, and inverse logit for binary and ordinal measures), Z_{ij} is a possibly time-varying vector of covariates (e.g., sex, race, age, nicotine dependence, quit intentions), and y_{ij} is the outcome for the ith person at the jth repeated measure. This model will be used for evaluating Hypotheses 1 ($\mu_{InsN} = \mu_{InsY}$), 2 ($\mu_{PicN} = \mu_{PicY}$), 3a ($\mu_{PicN,InsY} = \mu_{PicY,InsY}$) & 4a ($\mu_{PicY,InsY} = \mu_{PicY,InsY}$) as shown in Table 5.

Table 5. Hypotheses evaluated using Model 1 and associated tests

Hypothesis	Test
Hypothesis 1	$H_0^1: \beta_1 + \beta_2 = \beta_3 + \beta_4$
Hypothesis 2	$H_0^2: \beta_1 + \beta_3 = \beta_2 + \beta_4$
Hypothesis 3a	$H_0^{3a}: \beta_3 = \beta_4$
Hypothesis 4a	$H_0^{4a}: \beta_4 = \beta_2$

Allowing up to 20% missing data, the range of effect sizes for which we will have 80% power to reject hypotheses are given by the values in Table 6 for the data type outcomes and specified level of significance.

Table 6. Level of significance and detectable effect sizes for all hypotheses

Hypotheses	Outcome	Level of significance	Range of effects*
H1 & H2	Type 1	$\alpha = 0.05/6 = 0.0083$	0.15 - 0.17
	Type 2	$\alpha = 0.05/6 = 0.0083$	0.07 - 0.08
H3a, H3b, H4a, H4b, H5a, H5b, H6a, H6b	Type 1	$\alpha = 0.05/6 = 0.0083$	0.22 - 0.24
	Type 2	$\alpha = 0.05/6 = 0.0083$	0.10 - 0.11

^{*}range of effects is for the different amounts of missing data (i.e., 0% - 20%)

Model 2a and Model 2b:

$$y_{ij} = g^{-1} \big[\beta_0 + InsN_i \beta_1 + \, InsY_i \beta_2 + Z_{ij} \tau + \, \gamma_i + \epsilon_{ij} \big]$$

Where g^{-1} is the inverse link function (identity for continuous measures, and inverse logit for binary and ordinal measures), Z_{ij} is a possibly time-varying vector of covariates (e.g., sex, race, age, nicotine dependence, quit intentions), and y_{ij} is the outcome for the ith person at the jth repeated measure. The 2a and 2b models are stratified over whether pictures were included (2a) or not (2b). This model will be used to assess Hypothesis

 $3b - H_0^{3b}$: $\mu_{InsN} = \mu_{InsY}$. Associated power is shown in Table 6. Note that the stratified analyses in Models 2a and 2b are investigated only if H_0^{3a} is rejected.

Note: H_0^{3a} was never rejected.

Model 3a and Model 3b:

$$y_{ij} = g^{-1} [\beta_0 + PicN_i\beta_1 + PicY_i\beta_2 + Z_{ij}\tau + \gamma_i + \epsilon_{ij}]$$

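### Cigarettes per day is analysed as one log count per person, with no stated denominator and no offset for days observed

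*SAP*

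**What the plan says.** SAP Table 3 lists the secondary outcome as "Cigarettes Per Day (number of cig logs" and marks it in all eight hypothesis columns, H1 to H6b. Under Statistical design the SAP adds that "the one count measure that we evaluate (i.e., cigarettes per day) is a single measure for each person", so there are no repeated measures, and assigns "negative binomial regression with log link for count measures".

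Model 1 contains the four arm indicators, a covariate vector, a person effect and an error term. The covariate vector "is a possibly time-varying vector of covariates (e.g., sex, race, age, nicotine dependence, quit intentions"; days observed is not among the examples. No offset or exposure term appears anywhere in the SAP.

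The Missing Data section confines multiple imputation to evening-report outcomes. It explains that for cigarette surveys the authors could not separate not smoking from not reporting. It gives no rule for the logs themselves.

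On follow-up, Protocol 7.1 states that "EMA data were collected from participants over 14 days using a study smartphone", and Protocol 6 that "Participants could discontinue participation at any time". For measurement detail the SAP points elsewhere: "Details on the specific measures used and frequency of assessment are provided in the outcomes and results section of clinicaltrials.gov".

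**The concern.** A count needs a known period of observation. The outcome is named as a daily rate but described as a number of logs, and the model has nothing to carry the length of observation. On the natural reading, a day on which the phone was not used adds zero cigarettes, exactly as a smoke-free day does.

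Reduced consumption is one of the cessation outcomes named in H1. If participants in one arm stopped logging earlier, the model would show a fall in smoking that did not happen. If they stopped earlier in the comparison arm, a real fall would be masked. The protocol expects some smokers to avoid or react against pictorial warnings, so unequal disengagement is conceivable, but the documents give no evidence that it occurred.

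This is separate from cigarettes left unlogged on days when the person was taking part.

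**Working it through.** **There is no plan figure to reproduce.** The SAP gives no power or effect size for this outcome. Table 6 rests on 14 or 56 repeated measures, so it does not apply to a single value per person. Appendix 1 prints only outcomes not marked in Table 3, so it shows no cigarettes-per-day result.

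**Inputs from the documents.** Logging period: 14 days (Protocol 7.1). Analysed: 443 − 56 − 20 = 367 (Protocol 1).

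**Assumptions not in the documents.** The share *f* of an arm that stops early, the last day *k* of logging, and a constant smoking rate while logging.

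**One person.** Under a total, or a total over 14, the recorded rate is the true rate × *k*/14. A 20-a-day smoker who stops after day 7 has 7 × 20 = 140 logs, and 140/14 = 10 a day: half the true rate. For *k* = 10 the factor is 10/14 = 0.71; for *k* = 5 it is 5/14 = 0.36.

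**One arm.** The mean is multiplied by 1 − *f*(1 − *k*/14). With *k* = 7:

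- *f* = 5%: 1 − 0.05 × 0.5 = 0.975
- *f* = 10%: 1 − 0.10 × 0.5 = 0.950
- *f* = 15%: 1 − 0.15 × 0.5 = 0.925

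**Two arms, no true difference.** The apparent rate ratio is the ratio of these factors:

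- 5% versus 5%: 0.975/0.975 = 1.00
- 5% versus 10%: 0.950/0.975 = 0.974
- 5% versus 15%: 0.925/0.975 = 0.949

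**Effect on the test.** A simulation with no true effect used 600 runs, 183 people per group (about half of 367), an assumed mean of 15 cigarettes a day, an assumed between-person coefficient of variation of 0.4, and a two-sided 0.05 test. That level is for illustration; it is not the SAP's Bonferroni level.

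| Stopping early | Rate ratio, raw total | False positives, raw total | Rate ratio, with offset | False positives, with offset |
|---|---|---|---|---|
| 10% vs 10%, day 7 | 1.001 | 5.8% | 0.999 | 4.7% |
| 5% vs 15%, day 7 | 0.950 | 20.7% | 1.001 | 4.5% |
| 10% vs 20%, day 7 | 0.947 | 21.2% | 1.000 | 4.3% |
| 5% vs 20%, day 5 | 0.901 | 54.0% | 1.001 | 4.2% |

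The offset removes the artefact in each case. These rows show sensitivity to assumed stopping patterns, not the bias in this trial.

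**The case against.** The strongest reply is that the outcome is called cigarettes per day and its detail is deferred to the registry, so the value may already be logs divided by days observed. Early stopping would then not read as cutting down. That stands as a possibility: the SAP neither says it nor rules it out. Such a per-person mean would weight 5 days like 14, but this hardly matters. If the SAP's mean ICC of 0.73 applied to daily logs, the variance of a person's mean would be 0.73 + 0.27/5 = 0.784 with 5 days and 0.73 + 0.27/14 = 0.749 with 14, under 5% apart.

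A reader might infer that everyone who left early is counted as having cut down. The documents do not support that. "The final analytic sample involved 367 people" after 20 of 387 attendees (5.2%) failed minimum criteria that are not defined. Protocol 6 discontinued people who logged nothing and replaced withdrawals, without saying whether their partial data are analysed. The point concerns partial loggers who remained in the analysis.

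A reader might also take the SAP's 0–20% missing-data range as days lost by arm, and compute 0.80/0.90 = 0.89 from 20% versus 10%. That range is a power-planning allowance. With stopping at day 7, those losses would need 40% versus 20% of analysed participants to stop halfway, which sits poorly with real-time compliance monitoring and the check-in calls in Protocol 4.1.

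Finally, Model 1 is a template with an open covariate list, so its silence is not proof. Even so, days observed entered as an ordinary covariate is not an offset, and neither is mentioned.

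**Conclusion.** The gap is real. The SAP specifies a single number of logs per person in a log-link count model without a denominator or exposure term, and no missing-data rule covers logs. Taken as a total, or as a total over 14, partial loggers are recorded below their true rate, by half if they stop after day 7.

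It does not follow that the treatment comparison is biased. That requires early stopping to differ by arm, and the documents give no such figures. Under assumed imbalances of 5% versus 10% or 15% at day 7, the spurious rate ratio is about 0.97 or 0.95; with equal stopping it is 1.00 and the cost is noise. If logs were divided by observed days, the artefact is absent and only the description needs correcting.

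The outcome is secondary and no primary outcome is touched. Because it is marked for every hypothesis and the remedy is cheap, the change should be made.

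**What to change.** State how the value is built: a total, a total over 14, or a total over observed days. Unless it is already the last, do one of the following:

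- keep one record per person and add log(number of observed days) as an offset in the negative binomial model; or
- model daily log counts by mixed-effects negative binomial regression with a person-level random effect.

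Count a day as observed if it has at least one log or a filed evening report. A day with a report and no logs is zero; a day with neither is missing. Report observed days by arm.

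This rule depends partly on the outcome, because it drops smoke-free days with no report and so tends to raise estimated consumption. Add a sensitivity analysis that counts every day up to the participant's last recorded activity as observed.

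The cost is SAP wording and re-running this outcome's models on data already held. The estimate may become slightly less precise or less favourable, and it relies on a missing-at-random assumption for unobserved days.

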- Type 1 data (daily log data) were collected from each person across a 2-week period yielding up to 14 repeated measures per person. Daily log data include a range of primary outcomes (e.g., foregoing cigarettes, talk about cessation) and secondary outcomes (e.g., cognitive elaboration of cessation benefits, perceived susceptibility) that encompass binary, ordinal and continuous variables.
- Type 2 data (event-based EMA) were collected approximately 4 additional occasions per day per person, yielding an average of 56 repeated measures of event-related data per person. Event-related data include both primary outcomes (e.g., feeling about smoking, self-efficacy to quit smoking, motivation to quit smoking) and secondary outcomes (e.g., hopefulness about quitting, satisfaction from smoking) measured as ordinal and continuous variables.

Study hypotheses and outcomes of interest:

Table 2 shows the study hypotheses. The outcomes evaluated depended on the specific hypothesis. Behavioral and psychosocial outcomes that are more proximal to cessation behaviors (e.g., foregoing/stubbing out cigarettes;

Table 2. Study 1 Hypotheses: EMA Randomized Controlled Trial

Main effects of condition on cessation-related outcomes & primary mediators

- **H1:** Exposure to packs with inserts will result in stronger efficacy beliefs (e.g., self-efficacy, response efficacy) than packs without inserts, which, in turn, will lead to stronger cessation-related outcomes (e.g., interpersonal discussions about quitting, foregoing cigarettes, reduced consumption, intention to quit).
- **H2:** Exposure to packs with large pictorial HWLs will produce stronger negative affective responses toward smoking than text-only HWLs, which, in turn, will lead to stronger cessation-related outcomes (see H1).

Interactions between inserts and HWLs & explanatory mechanisms

- H3: Insert effects on cessation-related outcomes (see H1) will be stronger when accompanied by pictorial HWLs than by text-only HWLs, because pictorial HWLs will promote greater attention to inserts ("spotlight" effect of negative affect).
- H4: Pictorial HWL effects (relative to text-only HWLs) on cessation-related outcomes (see H1) will be stronger when accompanied by inserts, because inserts will promote efficacy beliefs and thereby reduce defensive responding.

Interactions between condition & smoker characteristics

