We use the numbers in Table 4 as inputs for independent observations in deriving the detectable effect. In what follows, we report ranges of detectable effect sizes from 0% to 20% missing data in complete-case analyses. This presentation notwithstanding, our data analysis will employ multiple imputation methods to replace missing data, and we will investigate sensitivity models to determine whether missingness is related to any of the outcomes or covariates (See **Missing Data**, below).

Alpha: Modifications of the level of significance are considered using Bonferroni adjustment to maintain an overall 0.05 level of significance. As most of our hypotheses involve assessing 6 primary outcomes for each of the two data types, we use a Bonferroni-corrected $\alpha = 0.05/6 = 0.0083$.

Effects size referents: We follow Cohen's standardized effect sizes of small=0.20, medium=0.50, and large=0.80.¹ Standardized effect sizes are absolute differences divided by the standard deviation.

Power: Power was fixed to 80% in all analyses.

Analyses: Most detectable effect sizes were calculated using PASS 2012 software from NCSS (Kayesville, Utah). The only exception is for a hypothesis of mediation. In that case, we used the *powerMediation* package for *R* software. Specifically, we utilized the *minEffect.SLR* method to determine the minimum detectable slope (effect).

All detectable effect sizes were calculated for power=80% and stated level of significance. Furthermore, we assessed detectable effect sizes for the planned data collection design, up to 10% missing data, and up to 20% missing data (see Table 4).

Statistical design:

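### Table 6 of the SAP does not apply to cigarettes per day, which has one value per person, and the SAP gives no valid power for that outcome

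*SAP*

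**What the plan says.** The SAP's Study design overview recognises two data types. Type 1 data "were collected from each person across a 2-week period yielding up to 14 repeated measures per person"; Type 2 averages 56 per person. Table 4 builds every power input from these counts (160\*14, 80\*14, 160\*56, 80\*56), discounted to 3N/7 under an assumed autocorrelation of 0.40.

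Table 6 is headed "Level of significance and detectable effect sizes for all hypotheses". The sentence above it gives it as the range of effects detectable with 80% power under Model 1, and Model 1's link list includes a log link for counts. On power in general the SAP says: "Power was fixed to 80% in all analyses". Alpha is 0.05/6, with the reason: "As most of our hypotheses involve assessing 6 primary outcomes for each of the two data types".

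Table 3 lists "Cigarettes Per Day (number of cig logs" as a secondary outcome, with a mark in all eight hypothesis columns from H1 to H6b. Statistical design says of this one count outcome: "i.e., cigarettes per day) is a single measure for each person and so there are no repeated measures". No separate power figure is given for it.

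**The concern.** An outcome with one value per person has 160 v 160 values for the main effects and 80 v 80 for the H3a and H4a cell comparisons. The Type 1 rows of Table 6 use 960 v 960 and 480 v 480 effective observations, and the Type 2 rows use four times as many. The figures for repeated measures therefore cannot be carried over to cigarettes per day.

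This matters because cigarettes per day is the measure of the reduced consumption named in H1, and the later hypotheses refer back to H1's outcomes. A reader who has only Table 6 could take a null result as evidence against effects of 0.15-0.17 SD (H1/H2) or 0.22-0.24 SD (H3a/H4a), which the analysis of persons was not sized to detect.

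**Working it through.** **Inputs from the SAP.** Persons per group: 160 (H1/H2) and 80 (H3a/H4a), from Tables 1 and 4. Power 80%. Alpha 0.05/6 = 0.0083. Printed Type 1 effects 0.15-0.17 and 0.22-0.24; printed Type 2 effects 0.07-0.08 and 0.10-0.11.

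**Assumptions added here.** Tests are two-sided (the SAP says only "Evaluation of hypotheses will involve inference from Wald tests of associated regression parameters"). Comparisons are of two means, unadjusted, by normal approximation. The effect is scaled on the SD of the per-person value.

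**Formulas.** Detectable effect = (z for alpha + 0.842) × √(2/n). Power = Φ(d/√(2/n) − z for alpha). The z value is 2.638 at alpha 0.0083 and 1.960 at 0.05.

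**Step 1: reproduce Table 6.** The multiplier is 2.638 + 0.842 = 3.480. With Table 4's effective sizes as n per group, at 0% and 20% missing data:

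| Row | n per group | Computed | Printed |
|---|---|---|---|
| H1/H2, Type 1 | 960, 768 | 0.159, 0.178 | 0.15-0.17 |
| H1/H2, Type 2 | 3,840, 3,072 | 0.079, 0.089 | 0.07-0.08 |
| H3-H6, Type 1 | 480, 384 | 0.225, 0.251 | 0.22-0.24 |
| H3-H6, Type 2 | 1,920, 1,536 | 0.112, 0.126 | 0.10-0.11 |

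The match is approximate. It is close enough to show that Table 6 rests on the repeated-measures counts.

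**Step 2: one value per person.** √(2/160) = 0.1118 and √(2/80) = 0.1581.

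| Contrast | Alpha | Effect for 80% power | Power at printed Type 1 effects |
|---|---|---|---|
| 160 v 160 (H1/H2) | 0.0083 | 3.480 × 0.1118 = 0.39 SD | 9.7% at 0.15; 13.2% at 0.17 |
| 80 v 80 (H3a/H4a) | 0.0083 | 3.480 × 0.1581 = 0.55 SD | 10.6% at 0.22; 13.1% at 0.24 |
| 160 v 160 (H1/H2) | 0.05 | 2.802 × 0.1118 = 0.31 SD | 26.8% at 0.15; 33.0% at 0.17 |
| 80 v 80 (H3a/H4a) | 0.05 | 2.802 × 0.1581 = 0.44 SD | 28.5% at 0.22; 32.9% at 0.24 |

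Worked case: 0.15/0.1118 − 2.638 = −1.296, and Φ(−1.296) = 9.7%.

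**Step 3: variants at alpha 0.0083.**
- Read against the Type 2 effects, power is 2-3%.
- One-sided testing gives about 15-19% at the Type 1 effects.
- With the 367 people analysed (Protocol Summary; equal arms assumed), the H1/H2 detectable effect is 0.36 SD and power is 11.5-15.6%.

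**Step 4: moderation contrasts at alpha 0.0083.** Assume an even split on the moderator. H5a/H6a compare four groups of 80, so the standard error is √(4/80) = 0.224 and power at 0.22-0.24 is about 5-6%. The H5b/H6b tests as written in Table 7 use four cells of 40, so the standard error is √(4/40) = 0.316 and power is about 3%. The full three-way contrast over eight cells of 40 gives about 2%.

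**Step 5: sensitivity to the SD scale.** If the single value were a 14-day mean and the effect were scaled on a single-day SD, the SD of the mean is √((1+13ρ)/14) under exchangeable correlation. At ρ = 0.73, the SAP's observed mean ICC, this is 0.866 and power is 14-19%. At ρ = 0.40 it is 0.665 and power is 27-36%. Under the SAP's own effective-size formula (14 × 3/7 = 6 per person) it is √(1/6) = 0.408 and power is 74-86%. All are at alpha 0.0083 with 160 or 80 per group.

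**The case against.** The strongest reply is that this is an omission and not a wrong figure. The sentence introducing Table 6 ties it to outcomes of the two data types, neither of which is described as containing counts. Cigarettes per day is named in neither list of examples, and the SAP is open that it has no repeated measures. This stands in part. A reader might infer that the SAP claims 80% power for cigarettes per day by name; it does not. But the SAP describes only two data types, promises power for each hypothesis, and attaches Table 6 to a model with a count link. Nothing tells the reader that Table 6 excludes this outcome.

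The alpha objection also stands. The 0.0083 level is derived from primary outcomes and this outcome is secondary, so the 10-13% figure should not be quoted without the 27-33% at 0.05.

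A reader might also infer that no treatment of within-person correlation could make Table 6 apply. The documents do not support that. The value is built from cigarette logs over 14 days, how it is formed is not stated, and on scaling the SAP says only "Standardized effect sizes are absolute differences divided by the standard deviation". Step 5 shows that one combination, a 14-day mean scaled on a single-day SD under the SAP's own formula, brings power back near 80%. The SAP states none of those choices.

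The planned model is a covariate-adjusted negative binomial regression, not a comparison of means. The documents give no explained variance. If covariates explained 30-50% (an assumption, on the linear scale), the H1/H2 detectable effect would be 0.389 × √0.7 = 0.33 down to 0.389 × √0.5 = 0.28 SD at 0.0083, or 0.26 down to 0.22 SD at 0.05. All still exceed the printed 0.15-0.17.

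Finally, the trial is complete, the section describes pre-data assumptions, and a reported confidence interval is a better guide to a null result than planned power. That is fair and limits the consequence. Appendix 1, however, covers only outcomes without a mark in Table 3, so it holds no interval for cigarettes per day.

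**Conclusion.** The point holds in this form: Table 6 cannot be applied to cigarettes per day, and the SAP gives no valid power for it. On a person-level SD, unadjusted and two-sided, the effects needed for 80% power exceed the upper printed Type 1 effects by a factor of about 2.3 at alpha 0.0083 (0.389/0.17 and 0.550/0.24) and about 1.8 at 0.05 (0.313/0.17 and 0.443/0.24).

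Two wider inferences are not supported. The 10-13% is not a figure for every hypothesis; it belongs to the simple two-group contrasts at the Type 1 effects and alpha 0.0083. And this point says nothing against the power of the primary outcomes, all of which have repeated measures. It concerns one secondary outcome, and its exact size depends on the alpha, the SD scale and the covariate adjustment, which the SAP leaves open for this outcome.

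**What to change.** 1. State that Table 6's Type 1 and Type 2 rows cover only outcomes with repeated measures.
2. Add a row for cigarettes per day computed on persons. It should name the alpha used for this secondary outcome, the SD on which the effect is scaled (and how the 14 days of logs become one value), and the contrast, including H5 and H6. On the assumptions above, the entries would be about 0.39 SD (H1/H2) and 0.55 SD (H3a/H4a) at alpha 0.0083, or 0.31 and 0.44 SD at 0.05.
3. Add one sentence saying that a null result on cigarettes per day does not exclude effects of the size printed in Table 6.

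The cost is one table row and two sentences, and a less favourable stated detectable effect for this outcome. Data, models, enrolment and the primary outcomes do not change.
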